2. PROTOCOL REVISION HISTORY

Date	Description
18 July 2017	Original Draft 0.1
30 Aug 2017	Draft 0.2
18 Sep 2017	Draft 0.3
26 Sep 2017	Draft 0.4
03 Oct 2017	Draft 0.5
17 Oct 2017	Draft 0.6
23 Oct 2017	Draft 0.7
13 Feb 2018	Draft 0.8
16 Feb 2018	Final 1.0
14 March 2018	Version 2.0 Sections 9.1, 10, 12.7, modified in response to GNA letter
12 December 2018	Administrative changes to Sections 3, 12.1, 12.2, 13.1, 15.4 and 18 Change in PD laboratory and correction of inconsistencies. Transcription error in the EUDRACT number corrected.
02 January 2019	Total blood volume draw corrected, correction of typographical Error Section 13

24 HOUR SPONSOR MEDICAL MONITOR

[REDACTED]

SAFETY REPORTING

[REDACTED]

SAFETY LABORATORIES

[REDACTED]

STATISTICS

[REDACTED]

ANALYSIS OF PHARMACODYNAMIC BLOOD SAMPLES

[REDACTED]

And

[REDACTED]

[REDACTED]

	
 • Geometric mean fold increase in antibody concentration. • Seroconversion rate (proportion of subjects with fold increase above threshold at any time post vaccination). • Proportion of subjects achieving antibody concentrations above specific thresholds at Days 29 & 85 (these will be 2, 4, 8 µg/mL). This will provide an assessment of the immune response to the first and second doses. 									
Study Design:	
This is a Phase I, randomised, double-blind, placebo-controlled, parallel group, single centre study.
 
There will be 2 cohorts of 30 subjects. Cohort 1 will receive two 0.5 mL injections, 4 weeks apart, each consisting of 25 µg of GBS-NN and 25 µg of GBS-NN2 (24 subjects) or placebo (6 subjects). Cohort 2 (30 subjects) will receive two 0.5 mL injections, 4 weeks apart, each consisting of 50 µg of GBS-NN and 50 µg of GBS-NN2 (24 subjects) or placebo (6 Subjects). All vaccines will be adsorbed to 500 µg Al3+ as Alhydrogel®.
 
Safety will be assessed after all subjects have completed Visit 4 (Day 8) for Cohort 1, at which point the decision will be made as to whether proceeding with administration of the doses in cohort 2 is appropriate.
									
Study Duration:	Study start is defined as check-in to the study unit on Day 1. Each individual subject will be involved in the study for approximately 12 weeks (excluding the 28 day screening period and the 6 month safety follow up).									
Study Population:	60 healthy female subjects aged 18 to 40 will be randomised into 2 cohorts of 30 subjects.									
Investigational Medicinal Product and mode of administration	
GBS-NN/NN2 vaccine will be supplied [REDACTED]
 
The placebo vaccine will contain Alhydrogel® mixed with sterile dilution buffer.
									
Selection of Doses	
The GBS-NN/NN2 vaccine will be supplied a [REDACTED]
 
The placebo vaccine will contain Alhydrogel® mixed with sterile dilution buffer.
 
[REDACTED]
 
Individual subject treatments will be dispensed by the pharmacist or designee and labelled in accordance with Annex 13 of “The Rules Governing Medical Products in European Community, volume 4 Good Manufacturing Practice for Medicinal Products”.
 
The following dosing strategy will be employed:
 
  
 Cohort	Dose schedule	Dose level GBS-NN/NN2 or placebo	
   
 1	Day 1, 29	25µg of each protein or placebo	
 
 2	Day 1, 29	50µg of each protein or placebo	
  
	Cohort	Dose schedule	Dose level GBS-NN/NN2 or placebo	1	Day 1, 29	25µg of each protein or placebo	2	Day 1, 29	50µg of each protein or placebo
Cohort	Dose schedule	Dose level GBS-NN/NN2 or placebo								
1	Day 1, 29	25µg of each protein or placebo								
2	Day 1, 29	50µg of each protein or placebo								
Treatment Schedule	Volunteers will provide written informed consent and will be screened for eligibility within 28 days before first study vaccine administration (Day 1). Study start is defined as check-in to the study unit on Day 1. Each individual subject will be involved in the study for approximately 12 weeks (excluding									

	
the 28-day screening period and the 6-month safety follow up). Eligible Subjects will be administered the primary dose of the appropriate dose of GBS-NN/NN2 or placebo according to the cohort and dosing schedule described in section 10.1. at Visit 2 and a second dose will be administered at Visit 6. All cohorts will incorporate sentinel dosing of 2 subjects in each cohort for the primary dose only: 1 on active treatment and 1 on placebo. No further subjects in that cohort will be dosed until 24 hours after dosing the second subject, provided that there are no serious or unexplained safety issues as determined by the Investigator.
 
The decision to proceed with administration of the primary dose in the subsequent cohort will be made as described in Section 12.5.
 
A safety follow-up visit will be performed 6 months (± 2 weeks) following the second study vaccine administration to check the general health collect blood for haematology, biochemistry and to assess the immune response. of the subject and to review adverse events (AEs).


Statistical Analysis:
	
Statistical analyses will be performed by [REDACTED] using SAS 9.3 or higher. Descriptive statistics for quantitative parameters will be provided using number of observations (N), mean, standard deviation (SD), minimum, median and maximum. Descriptive statistics for qualitative parameters will be provided using absolute frequencies (n) and relative frequencies (%). For immunological endpoints (IgG concentration and fold increase) additionally geometric means with corresponding 95% confidence intervals will be presented.
 
Demographic, baseline characteristics and data recorded during the study will be summarized using descriptive statistics by treatment (placebo or vaccine) and dose group, unless otherwise specified. Individual data will be presented as a data listing, sorted by treatment and administered dose level.
 
For parameters with evaluation before vaccination and in case of re-checked value(s), only the last observation prior to dosing will be used in descriptive and inferential statistics and derivations of other parameter values. After vaccination, only values of scheduled assessments (planned in the protocol) will be used.
 
Statistical tests will be carried out to compare results between treatment groups, depending on studied variable type. These analyses will be fully detailed in the SAP.
 
For categorical endpoints, such as local and systemic reactogenicity, a comparison of events intensity (scores) between vaccine dose groups can be performed with an adequate statistical test dealing with categorical variables (for example: Fisher exact test, Chi square test or generalized estimating equations).
 
For continuous endpoints, such as immune response induced by different GBS-NN/NN2 vaccine dosing regimens, appropriate statistical method (for example: ANOVA or ANCOVA) can be used to compare pre-vaccination and post-vaccination levels as well as post-vaccination levels between groups.

5. LIST OF ABBREVIATIONS

AE	Adverse Event
ALP	Alkaline Phosphatase
ALT	Alanine Aminotransferase
AST	Aspartate Aminotransferase
ATC	Anatomic and Therapeutic Class
AUC	Area Under the Curve
BMI	Body Mass Index
CA	Competent Authority
CPS	Capsule Polysaccharide
CRF	Case Report Form
CRO	Contract Research Organisation
CS	Clinically Significant
EC	Ethics Committee
ECG	Electrocardiogram
ELISA	Enzyme-Linked Immunosorbent Assay
EOD	Early Onset Disease
EU	European Union
FACS	Fluorescence-Activated Cell Sorting
FSH	Follicle Stimulating Hormone
GBS	Group B Streptococcus
GBS-NN	Group B Streptococcus vaccine component no 1
GBS-NN2	Group B Streptococcus vaccine component no 2
GCP	Good Clinical Practice
GGT	Gamma-Glutamyl Transferase
GMT	Geometric Mean Titre
HIV	Human Immunodeficiency Virus
IAP	Inter Partum Antibiotic Prophylaxis
ICF	Informed Consent Form
ICH	International Conference on Harmonisation
IMP	Investigational Medicinal Product
IG	Immunogenicity Set
IS	Included Set
IUD	Intra Uterine Device
LDH	Lactate Dehydrogenase
LLOQ	Lower Limit of Quantification
LOD	Late Onset Disease

MedDRA	Medical Dictionary for Regulatory Activities
NCS	Not Clinically Significant
NTEAE	Non Treatment Emergent Adverse Event
OPA	Opsonophagocytic Killing Assay
PBMC	Peripheral Blood Mononuclear Cell
PP	Per Protocol Set
PT	Preferred Term
SAE	Serious Adverse Event
SAF	Safety Set
SAP	Statistical Analysis Plan
SD	Standard Deviation
SDV	Source Data Verification
SEM	Standard Error of the Mean
SMB	Safety Monitoring Board
SOC	System Organ Class
SS	Safety Set
SUSAR	Suspected Unexpected Serious Adverse Reaction
TEAE	Treatment Emergent Adverse Event
Th cells	T helper cells
TOPS	The Over Subjecting Prevention System
VIS	Subject Information Sheet

6. INTRODUCTION

6.1 Background

Group B Streptococcus (GBS) has now emerged as the leading cause of neonatal sepsis and is also increasingly recognised as an important cause of disease in adults, especially in the elderly and those with underlying disease (Schrage et al., 2000, Skoff et al., 2009). In fact, GBS is responsible for 50% of life-threatening infections in newborns, leading to severe morbidity and life-long disabilities. In particular, GBS is responsible for over 80% of meningitis in neonates less than 2 months of age (CDC, 2010 Vol.59).

GBS neonatal infections are associated with high morbidity and mortality and constitute a major public health problem affecting 0.5 to 3 new-borns per 1000 live births (CDC 2002). In the UK, national surveillance during 2000-2001 identified a total of 568 cases; an incidence of 0.72 per 1000 live births, showing regional variation with 0.42 per 1000 live births in Scotland and 0.9 in Northern Ireland. GBS neonatal infections have been reported in and across Europe, USA, Australasia, South Africa, Kenya and Malawi confirming the global nature of the disease.

GBS related neonatal morbidity can be classified into Early Onset Disease (EOD; occurring 1 to 6 days after birth), and Late Onset Disease (LOD; occurring 7 to 89 days after birth). EOD accounts for about 60 to 70% of GBS related neonatal morbidity as a result of vertical transmission of GBS from mother to infant at or around the time of delivery. In over 90% of cases, clinical features of sepsis and pneumonia occur within 12 to 24 hours (Heath et al., 2004, 2009). In contrast LOD, which occurs 7 to 89 days post-delivery, and is acquired perinatally, nosocomially or from community sources, presenting with meningitis in up to 50% of cases (Heath et al., 2004). There is also an association with GBS urinary tract infection and the occurrence of chorioamnionitis, and premature labour (Anderson et al., 2007; Thomsen et al., 1987).

Introduction of inter partum antibiotic prophylaxis (IAP) in the year 2000 in birthing women, who are at risk of transmitting GBS to the infant during childbirth due to vaginal/rectal colonisation with GBS or other known risk factors, has reduced the incidences of EOD by up to 80% in countries, like the US, where universal antenatal screening programs for GBS colonization during pregnancy have been implemented. Other countries rely on risk assessment based on the factors outlined above, rather than universal screening for GBS colonization. On average GBS screening or risk-assessment results in some 20 to 50% of birthing women receiving IAP, depending on region.

Despite this widespread use of IAP, EOD has not been reduced by more than 80% at the most, and still affects some 4,500 new-born babies annually in Europe and the US combined; and the incidences have recently been on the rise again (Health Protection Agency UK, 2012 Vol.6). The failure of IAP to fully eradicate EOD relates primarily to lack of adherence to protocol, poor implementation of protocols, premature delivery, and childbirth lasting less than the 4 hours required for IAP to be fully active.

Importantly, the serious LOD infections (>50% meningitis) have remained unaffected by IAP, at 3,000 cases annually, due to the fact that nosocomial infections are unaffected by IAP during childbirth. Also, IAP has had no effect on the incidences of GBS induced stillbirths (900) and premature deliveries (7,000), which occur prior to administration of IAP.

In addition to the inability of IAP to completely eradicate EOD and in anyway prevent GBS-induced LOD, stillbirth and preterm labour, the widespread use of antibiotic prophylaxis in GBS prevention has resulted in the emergence of antibiotic resistance in GBS. Penicillin remains the preferred antibiotic prophylaxis, but clinical isolates with reduced sensitivity to penicillin due to mutations in penicillin-binding proteins have emerged over recent years (CDC, 2010 Vol.59)

(Kimura, 2008 Vol.52). The alarming finding is that the emerging patterns of mutations are identical to those observed in *S. pneumoniae* prior to the breakthrough of widespread true penicillin resistance in that pathogen (Dahesh, 2008 Vol. 52) (Nagano, 2008 Vol.52). Full breakthrough of penicillin resistance in GBS will lead to a dramatic increase in the incidences of EOD, potentially returning the world to pre-IAP levels, as well as creating a serious problem when having to treat such infections. In addition, wide-spread resistance to antibiotics other than penicillin already exists in GBS isolates (CDC, 2010 Vol.59). Finally, IAP has also led to an increase in neonatal infections with antibiotic resistant strains of other bacteria such as *E.coli*.

6.2 Rationale for Study

A large medical need exists for the development of an effective alternative to IAP for the prevention of neonatal GBS infections, as outlined above and a maternal vaccine would be the appropriate solution.

Immunization of pregnant women during the latter part of pregnancy leading to passive immunization of the unborn child through trans-placental transfer of protective GBS-specific antibodies would be beneficial. Such antibodies will likely persist for 3-6 months after birth and potentially protect the foetus in-utero, against GBS induced still birth and premature delivery; and the newborn baby against both EOD and LOD. A vaccine therefore seems the obvious choice for an alternative to IAP (Madhi et al 2016, Donders et al 2016, Heyderman et al 2016).

A number of GBS serotypes can be distinguished based on their type-specific capsular polysaccharides (CPS). This capsule represents a major virulence factor, which helps bacterial invasion by interfering with phagocytic clearance except in the presence of type specific opsonophagocytic antibodies (Baker 2000, Nizer et al., 2000). To date, 10 antigenically unique GBS serotypes have been identified (Ia, Ib, II-IX). Of these serotypes Ia, III and V are the most prevalent in EOD with type III accounting for 36% of EOD and 71 % of LOD, and together, serotypes Ia, Ib, II, III and V cover approximately 95% of all isolates.

Spontaneous colonization of women with GBS is the likely explanation for the existence of naturally occurring antibodies against several GBS antigens in pregnant women. Interestingly, the presence of high levels of anti-CPS antibodies in pregnant women has been found to correlate with protection of their off-spring against invasive GBS disease, indicating that vaccine-induced maternal anti-CPS antibodies would indeed be protective (Baker and Kasper, 1976; Lin et al., 2001; Lin et al., 2004).

MinervaX has developed a novel GBS vaccine candidate, GBS-NN, based on the N-terminals of the Rib and AlphaC surface proteins of GBS. Rib and AlphaC, and cross-reactive Alpha-like proteins (Alp I and Alp2/3; Alp2 and Alp3 have an identical N-terminal domains) that are found on most isolates of serotypes Ia, Ib, II, III, IV, V, VI, VII and VIII, and antibodies directed against the vaccine were found to recognize 80-100% of 154 clinical isolates of serotypes Ia, Ib, II, III and V tested for antibody binding. Naturally occurring antibodies against the full-length Rib and AlphaC proteins are found in pregnant women, likely due to exposure to GBS from colonization, and such antibodies are efficiently transferred to their babies in-utero. Antibodies to Rib and AlphaC elicit protective immunity in animal models when administered with the standard adjuvant alum (Larsson et al., 1999).

The first clinical trial with GBS-NN, in healthy non-pregnant women, has shown the potential vaccine to be highly immunogenic well tolerated with a good safety profile. Investigations into the breadth of coverage of the GBS-NN vaccine against all GBS strains have identified the need for the additional antigens, Alp1, Alp2, and Alp3 to be included in a vaccine. GBS-NN2 contains the Alp1, Alp2 and Alp3 N-terminal proteins (Alp2 N and Alp3 N are identical) and has been added to GBS-NN. Hence, of the four different members of the targeted surface proteins that are found on different GBS bacteria, two are represented in GBS-NN and the remaining two in GBS-NN2. MinervaX has completed toxicology studies on the GBS-NN/NN2 vaccine, which is

now ready to move into clinical trials, in a population of healthy, non-pregnant female subjects.

6.2.1 Summary of Non Clinical Data

Mice have been dosed with GBS-NN with and without alum at doses ranging from 2µg to 64µg. [REDACTED] immune responses were elicited at all doses, with the antibody responses at doses of 4µg to 64µg in the presence of Alhydrogel® being indistinguishable from each other and showing a trend towards being higher than responses to 2 µg [REDACTED]. The addition of alum reduced the time taken for the peak immune response to be achieved, increased the magnitude of the immune response and increased the number of responders.

The local and systemic toxicity studies with GBS-NN/NN2 in rabbits and rats, respectively, did not identify any unexpected findings. [REDACTED]

The findings of the studies are in line with the findings GBS-NN alone and the changes seen in the animals were considered to be the pharmacological responses to the vaccine inducing an immune response. [REDACTED]

Overall the data indicate that it is appropriate to continue development and administer the GBS-NN/NN2 vaccine to healthy subjects.

Reproductive toxicology studies are being completed, preliminary data has not identified any adverse effect on fetuses or foetal development.

Immunogenicity studies with GBS-NN/NN2 have been undertaken in mice [REDACTED]. Immunisation with either GBS-NN or GBS-NN2 induces significant cross-reactivity with the heterologous antigen. Primary immunization with the combination of GBS-NN and GBS-NN2 gives similar responses to all four domains and the responses to homologous antigens are equivalent to those induced by immunizing with the single molecules.

6.2.2 Summary of Clinical Data

Study MVX13211 with GBS-NN alone, has shown that GBS-NN is well tolerated in healthy female subjects. The study concluded that GBS-NN has an appropriate safety profile for a vaccine with the primary adverse reaction of pain at injection site was mild and reported at an incidence comparable to other intramuscularly administered vaccines that contain Alhydrogel®. Healthy subjects developed high concentrations of antibodies against the N-terminal proteins AlphaC and Rib [REDACTED], if the antibodies are protective, it is anticipated that the foetus will be passively immunized from the mother.

The first clinical trial with GBS-NN, in healthy non-pregnant women, has shown the potential

vaccine to be highly immunogenic when 2 doses of 50 µg or one or two doses of 100 µg were administered with Alhydrogel®.

[REDACTED]

These studies have identified the need for the additional antigens, Alp1, Alp2 and Alp3 to be included in a vaccine. GBS-NN2 contains the Alp1, Alp2 and Alp3 N-terminal proteins (Alp2 N and Alp3 N are identical) and has been added to GBS-NN, in order to confer protection against all clinical isolates of GBS. Hence, of the four different members of the targeted surface proteins that are found on different GBS bacteria, two are represented in GBS-NN and the remaining two in GBS-NN2.

[REDACTED]

GBS-NN demonstrated a good safety profile with most adverse events (AEs) being mild and related to injection site reactions, no serious adverse events related to GBS-NN were reported. It is anticipated that the GBS-NN/NN2 vaccine will have a similar profile, as the two additional N-terminal proteins are very similar in structure to the original GBS-NN proteins. Animal toxicology studies showed similar toxicity profiles for GBS-NN and GBS-NN/NN2.

Cross reactivity with the other N-terminal proteins Alp1, Alp2 and Alp3 was not of the anticipated magnitude and the addition of these proteins is considered necessary to broaden the coverage of the vaccine against pathogenic strains of GBS. Hence, the GBS-NN vaccine will be investigated in a study of a similar design to Part B of MVX1321 I, as the initial study before moving to investigate safety in pregnant women.

6.3 Risk/Benefit Assessment

Antibodies against the full-length Rib, AlphaC, Alp1, Alp2 and Alp3 proteins, from which the GBS-NN and GBS-NN2 are derived to make up the vaccine antigens, naturally occur in women exposed to GBS, and such antibodies are efficiently transferred to the unborn child *in-utero*. Many adults and new-born infants have, therefore, already been naturally exposed to the proteins from which the antigen is derived and to antibodies against these proteins, and no side effects have been attributed as a consequence of such exposure in humans.

[REDACTED]

[REDACTED]. The maximum human dose will be 50 µg, which if administered to a 60 kg woman would equate to 0.83 µg/kg giving a safety margin of at least 60-fold.

The planned excipients in the vaccine formulation are also all well-known from other vaccines, and no novel or non-tested components are used. The proteins in the vaccine are adsorbed with a known adjuvant, Alhydrogel®, (0.5 mg of Al³⁺ per dose), corresponding to the dose used in many other commercial vaccines.

This is a new investigational product; therefore, there are currently no expected AEs related to the product. However, following injection of GBS-NN alone, approximately 30% of the subjects in the study experienced mild pain. Pain post-injection that is worse than mild would be considered to be unexpected. It is not anticipated that adding the two additional antigenic proteins, to GBS-NN, bound to Alum will significantly alter the safety profile. The Investigator is responsible for reporting adverse events (AEs) that occur during the course of the study. Serious adverse reactions that are deemed to be related to the investigational product in the proposed study will be reported as suspected unexpected serious adverse events (SUSAR).

GBS-NN/NN2, like other protein-based vaccines, may theoretically be associated with a transient febrile reaction (body temperature greater than 38.0°C but not greater than 38.7°C) following vaccination. Immune complex-mediated reactions are unlikely given the recombinant nature of GBS-NN/NN2, however, it is still possible that hypersensitivity may occur.

Based on the results from clinical use of other protein vaccines adsorbed to Alhydrogel®, and other aluminium containing adjuvants transient local reactions at the injection site, including pain, oedema, bruising, erythema and induration, mainly of mild intensity, are likely to occur. In addition, flu-like symptoms, such as fatigue, malaise, myalgia, and mild to moderate headache may occur.

The protocol requires that subjects are monitored after vaccine administration (vital signs and general signs and symptoms), with regular follow-up visits for physician assessment and questioning regarding AEs will be conducted for all subjects in the study. All study subjects will be monitored for potential side effects of vaccination during the entire course of the study, as per the protocol, and adverse events must be appropriately followed up.

GBS-NN/NN2 vaccination is contraindicated in subjects known to suffer hypersensitivity reactions to vaccines or a known allergy to aluminium hydroxide. For the purpose of the study subjects who have experienced a significant illness in the four weeks prior to check in will be excluded. The vaccine should not be given to subjects with known or suspected immune deficiency, autoimmune diseases or who have an acute infection.

GBS-NN/NN2 should not currently be given to women known, or suspected to be, pregnant, or to nursing mothers. Currently GBS-NN/NN2 should only be administered to women of child-bearing potential if adequate contraceptive precautions are taken, accompanied by serum and/or urine pregnancy testing prior to vaccination and during follow up.

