9.2 Exclusion Criteria

1. Subjects who have received GBS-NN vaccine previously.
2. Subjects with history or presence of significant cardiovascular disease, pulmonary, hepatic, gallbladder or biliary tract, renal, haematological, gastrointestinal, endocrine, immunologic, dermatological, neurological, psychiatric, autoimmune disease or current infection.
3. Pregnant or lactating females.
4. Laboratory values at screening which are deemed by the investigator to be clinically significantly abnormal.
5. Positive drug screen for drugs of abuse or a positive alcohol urine test prior to first dosing unless there is a documented medical explanation for the positive result other than drugs of abuse (e.g., the subject has been prescribed opioids for pain).
6. Positive for human immunodeficiency virus (HIV), hepatitis B or hepatitis C.
7. Participation in a clinical drug study during the 90 days preceding the initial dose in this study.

8. Any significant illness during the 4 weeks preceding check-in for this study (Day 1).
9. Subjects with a history of allergic reactions after previous vaccination.
10. Subjects who have received any vaccine within 30 days of screening, or who are planning to receive a vaccine up to Day 85 of the study.
11. Subjects receiving immunosuppressive therapy in the 6 months prior to screening, taking any short-term medications including over-the-counter (OTC) preparations, within 7 days of the first dose. Chronic medications such as antihypertensives, bronchodilators, oral contraceptives or statins that do not affect the immune system, will be permitted and allowed to continue during the study at the discretion of the Investigator. Paracetamol will be permitted for the treatment of headache or other symptoms. Use of OTC vitamins and dietary supplements is allowed
12. Subjects with tattoos at the proposed site of vaccine administration.
13. Donation of blood or blood products within 90 days prior to vaccine administration or intending to donate blood or blood products within 90 days of the last visit.
14. Subjects who, in the opinion of the Investigator, are unsuitable for participation in the study.

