10.3 Randomisation

Subjects will be randomised pre-dose on the morning of Day 1, once all eligibility criteria have been verified. A randomisation list will be held on site, which will be accessible only to unblinded study personnel.

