12.1 Screening Period

Screening assessments will be performed within 28 days prior to the first study vaccine administration (Day 1). The following assessments will be carried out at the screening visit (Visit 1) after written informed consent has been obtained:

- Inclusion/Exclusion
- Demography
- Medical history
- Physical examination
- Height, weight, body mass index (BMI)
- Vital signs (heart rate, blood pressure, oral temperature and respiration rate)
- 12-lead electrocardiogram (ECG)
- Urinalysis
- Blood samples for haematology and biochemistry
- Blood samples for HIV, hepatitis B and hepatitis C
- Serum pregnancy test for females of child-bearing potential
- Alcohol urine test
- Urine drugs of abuse test Cannabinoids, amphetamines, cocaine, benzodiazepines, opiates and cotinine.
- A review of all medications taken in the previous month

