16. ETHICS AND REGULATORY

16.1 Conduct

This study will be conducted in accordance with the standard operating practices of the Sponsor and Contract Research Organisation(CRO), which are designed to ensure adherence to Good Clinical Practice (GCP) guidelines as required by the following:

1. Declaration of Helsinki, 1964 (“Recommendations Guiding Physicians in Biomedical Research Involving Human Patients”), and all its accepted amendments to date concerning medical research in humans.
2. ICH E6 Guideline for GCP and subsequent notes for guidance (CPMP/ICH/135/95) European Agency for the Evaluation of Medicinal Products, Committee for Proprietary Medicinal Products, International Conference on Harmonisation of Pharmaceuticals for Human Use. (Note for Guidance on Good Clinical Practice, 2002).
3. European Union (EU) Clinical Trials Directive 2001/20/EC on the regulation of clinical trials in the EU and the implementation of GCP.
4. GCP Directive 2005/28/EC.

This study will be conducted in accordance with national and local laws (e.g. drug and narcotics laws) of the countries where study sites are located.

The Investigator agrees, when signing the protocol, to adhere to the instructions and procedures described in the protocol and to adhere to the principles of ICH Good Clinical Practice to which the protocol conforms as well as all governing local regulations and principles for medical research.

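### The aluminium hydroxide allergy contraindication in Section 6.3 is not carried into the eligibility criteria of Sections 9.1 and 9.2 that gate randomisation

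*Combined protocol and SAP*

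**What the plan says.** Section 6.3 (Risk/Benefit Assessment) says: "GBS-NN/NN2 vaccination is contraindicated in subjects known to suffer hypersensitivity reactions to vaccines or a known allergy to aluminium hydroxide". The two conditions are joined by 'or', so each is a contraindication on its own.

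Section 9.2 has one criterion on allergy, exclusion 9: "Subjects with a history of allergic reactions after previous vaccination". Two other exclusions could bear on the matter. Exclusion 2 covers significant disease in a list of systems that includes "endocrine, immunologic, dermatological, neurological, psychiatric, autoimmune disease or current infection". Exclusion 14 is the general clause: "Subjects who, in the opinion of the Investigator, are unsuitable for participation in the study".

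Section 10.3 ties randomisation to the eligibility list: "Subjects will be randomised pre-dose on the morning of Day 1, once all eligibility criteria have been verified".

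The synopsis states that every vaccine dose is adsorbed to 500 µg Al3+ as Alhydrogel. Of the control it says: "The placebo vaccine will contain Alhydrogel® mixed with sterile dilution buffer".

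Section 16.1 binds the site to the protocol as a whole: "The Investigator agrees, when signing the protocol, to adhere to the instructions and procedures described in the protocol".

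**The concern.** The sponsor has already decided that a woman with a known aluminium hydroxide allergy must not be vaccinated. The list that site staff verify on the morning of Day 1 does not contain that decision. If only the numbered criteria are worked through, a contraindicated woman can pass.

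What is at stake is her safety at entry. Both arms contain the adjuvant, so neither allocation avoids the exposure, and two injections are planned. The vital signs at 2 and 4 hours, the examination before discharge (Section 12.2) and the individual stopping criteria (Section 12.6) all operate after the dose. They can detect a reaction and limit its consequences, but they cannot prevent the exposure.

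**Working it through.** The plan states no figure on this point and no calculation applies. The check compares Section 6.3 with each listed criterion, then asks what else would keep the woman out.

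**Step 1. Which contraindications are carried over.**

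| Contraindication in the Section 6.3 sentence | Named in 9.1 (7 inclusions)? | Named in 9.2 (14 exclusions)? |
|---|---|---|
| Hypersensitivity reactions to vaccines | No | Yes, exclusion 9 |
| Known aluminium hydroxide allergy | No | No |

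One of the two is carried over. The inclusions cover age, BMI, weight, consent, menopausal status, pregnancy and contraception, and smoking. None concerns allergy. Among the exclusions, only number 9 does. Both lists are numbered without a break and show no redaction, so the missing item is not explained by blacked-out text.

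**Step 2. Who falls into the gap.** A known aluminium allergy can have come to light in two ways.

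- After an earlier vaccination: exclusion 9 removes her with no judgement needed.
- From another source, such as non-vaccine exposure or testing: exclusion 9 does not apply.

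The gap is the second group only.

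**Step 3. What would still keep the second group out.**

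- Section 6.3 itself. It is categorical, and Section 16.1 obliges the investigator to follow it, but it is not one of the criteria in Section 9.
- Exclusion 2. It requires the allergy to be read as significant immunologic or dermatological disease, which is a judgement.
- Exclusion 14. It is investigator opinion by its own terms.

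No specific listed criterion excludes her.

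**Step 4. Whether allocation matters.** The active doses and the placebo both contain Alhydrogel, so it does not.

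**Step 5. Whether screening would bring the allergy to light.** Section 12.1 introduces its list with "The following assessments will be carried out at the screening visit (Visit 1) after written informed consent has been obtained", and the list includes a medical history. Section 12.2 adds a general medical review at Visit 2 to re-confirm eligibility. Either gives the opportunity to ask. The protocol does not itemise the questions, and the case report form is not available, so whether allergy is asked about cannot be settled from these documents.

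**The case against.** The strongest reply is that the prohibition is already in the protocol. Section 6.3 leaves no discretion once the allergy is known, the investigator has agreed to follow the protocol, and dosing such a woman would breach it. On this view the fault is only that a binding rule is not repeated in a checklist. The reply adds that exclusion 9 removes the women whose allergy showed itself after a vaccine. Section 6.3 notes that the aluminium dose matches that of many commercial vaccines, so vaccination is a plausible way for such an allergy to appear. The requirement that subjects be healthy, exclusions 2 and 14, the Visit 1 history and the Visit 2 review are further layers.

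Much of this stands, and it rules out several stronger readings.

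- A reader might infer that keeping such a woman out rests only on investigator judgement, or that the protocol permits her to be vaccinated. Neither follows, because Section 6.3 forbids it outright and binds the investigator.
- A reader might size the problem by exposure, since all 60 planned subjects (2 × 24 = 48 active, 2 × 6 = 12 placebo) are assigned Alhydrogel. That counts everyone exposed, not those at risk, who are only women with a known aluminium allergy.
- A reader might infer that allergy is not asked about at screening. The text does not itemise the medical history, and that silence shows nothing either way.

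One point survives. A rule that must be satisfied before dosing is absent from the list whose verification opens the way to randomisation. Whether it is applied then depends on someone recalling a sentence in the risk/benefit section.

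**Conclusion.** The point holds as an inconsistency between a stated contraindication and the operative eligibility list. It is minor. One of the two contraindications in the Section 6.3 sentence has no matching criterion. The consequence is confined to women with a known aluminium hydroxide allergy and no earlier allergic reaction to a vaccine, and it arises only if Section 6.3 is overlooked and neither exclusion 2 nor exclusion 14 is used. The documents give no frequency for this group. That it is very small is an assumption, though a reasonable one in healthy volunteers aged 18 to 40.

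The conclusion also assumes that the criteria verified under Section 10.3 are those numbered in Sections 9.1 and 9.2, which is the natural reading. Sample size, power, analysis sets and the interpretation of results are not affected.

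**What to change.** Extend exclusion 9 in Section 9.2 by adding, after its present text, *or known allergy to aluminium hydroxide*. Confirm the item in the medical history already taken at Visit 1 (Section 12.1). Extending the wording to other components of the vaccine or placebo is optional, because the inconsistency shown concerns aluminium hydroxide only.

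The cost is one line in Section 9.2 and one question in an existing assessment. No visit, test or subject is added, and no new clinical judgement is needed because the sponsor has already stated the contraindication.
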